2.3 Data and Analysis Quality Control

The Data Management Plan (DMP) will detail the quality assurance and quality control systems to be implemented to assure the quality of the data. Similarly, the quality control of the statistical analysis will follow the standard procedures of the unit performing the statistical analyses.

3. PRIMARY VARIABLES

The primary safety endpoint will be the nature and occurrence of Serious Adverse Events (SAEs) and Adverse Events (AEs) including application of sick day rules and adrenal crises observed throughout the study.

The key secondary endpoints are:

- Growth velocity (linear growth velocity standard deviation score [SDS])
- Cortisol (all subjects) and adrenal androgen levels (17-OHP, A4, testosterone) in CAH subjects only

The safety variables include:

- AEs and SAEs
- Laboratory assessments
- Vital signs including weight and height

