	
Secondary endpoints:
 
 
• Standard deviation score (SDS) for height and weight
 
• Cortisol (all subjects) and adrenal androgen levels (17-OHP, A4, testosterone) in CAH subjects only
 

METHODOLOGY	
NUMBER OF SUBJECTS (PLANNED):	Maximum of 24 subjects
SUBJECTS:	Children who have successfully completed study Infacort 003
PRINCIPAL INCLUSION CRITERIA	
Subjects successfully completing study Infacort 003, whose inclusion criteria were:
 
 
1. Male and female children less than 6 years of age.
 
2. A diagnosis of AI as confirmed by an inappropriately low cortisol usually with other supporting tests.
 
3. Receiving appropriate adrenocortical replacement therapy (hydrocortisone with/without fludrocortisone).
 
4. Adequately hydrated and nourished.
 
 
In addition, the parents/carers must be able to understand and give written Informed Consent (according to AMG §40 (1) 3b) for this extension study.

PRINCIPAL EXCLUSION CRITERIA:	
 
1. Clinically evident acute AI (adrenal crisis) (Note: the subject can be re-evaluated for eligibility once the episode is over)
 
2. Inability of the child to take oral therapy
 
3. Subjects with clinical signs of acute infection or fever on inclusion (Note: the subject can be re-evaluated for eligibility once the episode is over)
 
4. Any surgical or medical condition that in the opinion of the Investigator may place the subject at higher risk from his/her participation in the study
 
5. Parents/carers of subjects unwilling to consent to saving and propagation of pseudonymised medical data for study reasons
 
6. Subjects who are in a dependent relationship with the Investigator or the Sponsor
 

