## 13.1 General considerations

Only descriptive statistical methods will be used for the statistical evaluation of this study (this includes CIs). All recorded and derived variables will be presented using standard procedures depending on the underlying distribution: for continuous data, sample size, mean, standard deviation (SD), minimum, median and maximum; for categorical data, sample size, absolute and relative frequency. The behaviour over time of continuous and categorical data will be analysed by presenting summary statistics for the actual values and change from baseline at each visit, if appropriate. No missing data will be replaced for any secondary variable.

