### 13.2.2 Secondary Variables

SDS for height and weight, cortisol (all subjects) and adrenal androgen levels (17-OHP, A4, testosterone) in CAH subjects only.

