### **13.3.2.2 Growth Velocity**

SDS for height and weight will be calculated for each subject using an age- and gender-matched German healthy reference cohort. Details will be described in the SAP.

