#### **Protocol Version 4.0 dated 20 July 2017**

The following changes were made to the protocol:

- 1) The Sponsor signatory was changed from [REDACTED]
- 2) Confirmed in Section 12.3.6 that AEs, whether or not they are considered serious, leading to the application of sick day rules and use of sick day medication and which lead to any medical intervention either sought or required, such as at a hospital/clinic, are to be considered to be AEs of special interest, In addition, any occurrence of adrenal crisis must be recorded as an AE of special interest.
- 3) In some cases, whilst the subject is cared for by Charité-Universitätsmedizin Berlin for the purposes of the study, it may be necessary of the Investigator at Charité-Universitätsmedizin Berlin to visit the subject at their local hospital. A detailed procedure for this scenario has been added as Appendix 6.
- 4) In line with the proposed labelling for Infacort®, the wording around administration of the granules was amended to say that the granules can be sprinkled onto a spoonful of yoghurt, fruit purees (e.g. apple sauce) or fruit mousses rather than using the term 'mixed'.
- 5) The protocol currently states that subjects can continue to be treated in this study until they meet the study withdrawal criteria, Infacort® is granted a marketing authorisation (and so is available commercially), Infacort® is refused a marketing authorisation, or the Sponsor decides to discontinue the study. A footnote has been added stating that at the time of submission of this amendment (protocol version 4.0), Infacort® is the subject of an ongoing Marketing Authorisation Application procedure and that for clarity, the end of study visits for each subject will occur after Infacort® is commercially available.
- 6) Published data are now available on the study conducted at Berlin on the lack of formal quality control of crushed tablets so the information has been updated in Section 5.4 (Rationale) and the formal reference added.
- 7) Added to Section 8.14 that if a visit needs to be postponed for more than 10 days, then the subject should attend for the visit before the period of absence for safety and drug supply reasons. Subsequent visits will then be scheduled at regular intervals from the revised early visit date.

- 8) Testing of hydrocortisonacetat in the blood spot analyses (Appendix 1) was removed since this is no longer analysed by the laboratory.

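### The SAP still analyses growth-velocity SDS as the secondary growth endpoint, although the current protocol has replaced it with height and weight SDS against a German reference

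*SAP*

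**What the plan says.** **Protocol (version 4.0).** The synopsis and section 7.2 give the secondary growth endpoint as "Standard deviation score (SDS) for height and weight". Section 13.2.2 repeats it among the secondary variables: "SDS for height and weight, cortisol (all subjects) and adrenal androgen levels". Section 13.3.2.2 fixes the type of reference, "SDS for height and weight will be calculated for each subject using an age- and gender-matched German healthy reference cohort", and then hands the rest over: "Details will be described in the SAP". The heading of that section nevertheless still reads "Growth Velocity". Appendix 7, under "Protocol Version 4.0 dated 20 July 2017", records that growth velocity was dropped as a secondary endpoint because the matched German reference mean and SD could not be obtained.

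**SAP.** Sections 1 and 6 give protocol versions 2.0 (September 2015) and 3.0 (July 2016) as the basis. Section 5.13 lists changes made for the July 2016 amendment only. Section 3 names "Growth velocity (linear growth velocity standard deviation score [SDS"]) as a key secondary endpoint. Section 5.10 gives its formula, Table 8.1 is its secondary results table, and Appendix 6 Listing 2 is its listing. Height and weight z-scores appear in section 5.11 with the safety variables, and in Table 12.2 under Safety Results. Section 5.1 adds general rules: derived variables are summarised by cohort and overall, and all derived data are listed.

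**The concern.** The protocol and the SAP name different secondary growth endpoints, and both statements are in current text. A programmer working from the SAP would produce growth-velocity SDS as the secondary growth result. The protocol's own endpoint would be filed among the vital-sign tables, with no statement that it is a secondary endpoint.

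The reference population is a second gap. An SDS has no meaning apart from the reference it is computed against. The protocol requires a healthy German cohort and relies on the SAP for the details, but the SAP says only that the reference is matched on age and gender. The choice of dataset would therefore be made at the analysis stage of an open-label study, when the data can already be seen.

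**Working it through.** No sample size, power or error-rate calculation is involved, so the check is a comparison of the texts.

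**1. Which protocol the SAP follows.** The latest protocol the SAP cites is version 3.0, dated 25 July 2016. Its latest dated reference is the data-monitoring SAP of January 2017. Protocol version 4.0 is dated 20 July 2017. The SAP text is therefore not written to version 4.0.

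**2. The growth endpoint in each document.**

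| Item | Protocol 4.0 | SAP |
|---|---|---|
| Secondary growth endpoint | Height SDS and weight SDS: synopsis, 7.2, 13.2.2 (3 places) | Growth-velocity SDS: section 3, section 5.10, Table 8.1, Appendix 6 Listing 2 (4 places) |
| Height and weight SDS named as secondary | Yes | No (0 places) |
| Where height and weight SDS are reported | Secondary variable | Safety: section 5.11, Table 12.2 |
| Reference | Healthy German cohort, matched on age and gender | Matched on age and gender; no country, dataset or version (0 of 2 derivations name one) |

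**3. Whether the SAP's secondary table can be produced.** Section 5.10 first computes GV = 12 × (H2 − H1) / D2, in cm/year, from the baseline and current heights and the months between them. It then computes Z = (GV − μ) / SD. The first step uses only study data. The second needs a reference mean μ and SD by age and gender. Appendix 7 of the protocol says these were not available for the German population and gives that as the reason for abandoning growth velocity. Table 8.1 therefore either cannot be produced against the German reference or requires some other reference that neither document names.

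**4. Whether other SAP text closes the gap.** Section 5.11 derives height and weight z-scores by visit, and section 5.1 supplies the cohort summaries and listings. The numbers would therefore exist. Nothing in those sections makes them the secondary endpoint, removes growth-velocity SDS from Table 8.1, or identifies the reference. Section 5.11 also gives no formula for the two z-scores.

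**5. Whether this rests on superseded text.** It does not. The conflict is between the body of the current protocol and the body of the SAP. The amendment history only explains how it arose.

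**The case against.** The strongest reply is that this is a matter of version timing. The SAP very probably predates version 4.0 and was correct when written, its section 1 says that later amendments may require changes to it, and a newer SAP may exist that is not among these documents. That explains the mismatch but does not remove it from the SAP in hand. If a later SAP exists and makes the change, citing it closes the point.

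Second, little would be lost. Height and weight z-scores are already planned by visit, no measurement is missing, and the analysis is purely descriptive. This stands, and it limits the consequence.

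Third, the protocol itself lists height and weight with the safety assessments (section 8.12.1), so a safety table is not out of place for them. That is fair for the raw measurements. The protocol still lists the SDS values as secondary endpoints, and the SAP gives that place to a different variable.

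Fourth, the SAP is read alongside the protocol, which already requires a healthy German cohort, and the SAP wording is compatible with that. This narrows the gap to the specific dataset and the method of calculation, which are the details the protocol left to the SAP.

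Fifth, the SAP allows uninformative tables to be omitted. That might remove Table 8.1 in practice, but it would not put the right endpoint in its place.

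**Conclusion.** The concern holds. On the documents provided, the SAP names, derives and tabulates a secondary growth endpoint that the current protocol has replaced, and it does not identify the reference for the endpoint that replaced it. The growth endpoint has to be realigned in four places in the SAP, and the reference population is unnamed in both z-score derivations.

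The effect is confined to one secondary endpoint. With at most 24 children and descriptive methods only, no test or error rate is affected, and the primary endpoint of adverse and serious adverse events does not change. The leftover heading in protocol section 13.3.2.2 is clerical and adds no weight. The conclusion assumes only that the SAP supplied is the operative one. It should be fixed before the final analysis.

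**What to change.** Amend the SAP as follows:

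- Cite protocol version 4.0 in sections 1 and 6, and record the change in section 5.13.
- In sections 3 and 5.10, Table 8.1 and Appendix 6 Listing 2, replace growth-velocity SDS with height SDS and weight SDS. Move the content of Table 12.2 to the secondary outputs.
- Name the healthy German reference dataset, with its version, and state how the SDS is calculated from it. Use the same reference wherever an SDS is reported.
- Raw growth velocity in cm/year may stay as a descriptive variable, since it needs no reference values.
- A summary of change in SDS is optional; protocol section 13.1 already allows "change from baseline at each visit, if appropriate".

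At the next protocol amendment, correct the heading of section 13.3.2.2 to match the text under it.

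The cost is a SAP amendment and one clerical protocol correction. Height and weight are collected at every visit, sex and date of birth come from Infacort 003, and the z-scores are already planned, so nothing further has to be collected from the children.

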4. SAMPLE SIZE JUSTIFICATION

No formal sample size calculation is provided for this study since only subjects who have previously been treated in study Infacort 003 can enter this study. Hence the maximum number of subjects in this study is 24.

5. METHODS OF ANALYSIS AND PRESENTATION

5.1 General Principles

The statistical analysis will be performed by a statistical unit, using SAS version 9.1 or later. Any statistical analyses not described in the protocol or in this SAP will be documented in the study report.

All recorded and derived variables will be presented by cohort and overall (and by visit, if appropriate) using appropriate descriptive summary tables (continuous data: sample size, mean, standard deviation (SD), minimum, median, maximum; categorical data: sample size, absolute and relative frequency). Missing data will be treated as missing and no attempts will be made to impute values for missing data. The behaviour over time of continuous and categorical data will be analysed by presenting summary statistics for the actual values and change from baseline at each visit, if

appropriate. Graphical presentations of the concentration data over time will also be provided. All collected and derived data will be listed. Specifically, data collected at unscheduled visits will be listed only and will be excluded from summary statistics.

In all summaries, the groups will be displayed in the following order: cohort 1, cohort 2, cohort 3 and overall. All collected information will be listed sorted by cohort and subject number for the safety population. Subjects who didn't receive study medication will be listed separately.

For all parameters, baseline is defined as the last available pre-treatment value (i.e. the last non-missing value available before Infacort® intake).

Only descriptive statistical methods will be used in the analyses of the data. In addition, due to the low number of subjects in this study and depending on the actually collected data some of the below described tables/analyses may not provide useful information. In this case tables/analyses will be omitted.

5.2 Definition of Analysis Populations

The following analysis sets will be used for the statistical analysis:

Screening Population	All subjects who were screened (i.e., gave informed consent)
Safety Population	The Safety Population will include all subjects who receive a complete or a partial dose of Infacort®.

Protocol Violations/Deviations

All protocol violations/deviations will be reviewed and classified as either 'minor' (unlikely to affect trial outcomes) or 'major' (likely to affect the trial outcome).

5.3 Disposition of Subjects

A summary of the subjects' disposition will be created including: number of subjects screened, number of screen failures, number of eligible subjects not treated, number of subjects treated in each cohort and overall, number of subjects who completed the study in each cohort and overall. In addition, a summary of the number and percentage of subjects in the safety population who discontinued the study and their reasons for discontinuation will be presented by cohort and overall.

5.4 Demographic and Baseline Characteristics

Demographic characteristics (age [days], gender and ethnic origin), body measurements (height, weight, Body Mass Index [BMI], Body Surface Area

[BSA] and causes for AI will be summarised by cohort and overall for the safety population.

Age (in days), BMI and BSA will be calculated as:

- Age (in days) will be calculated as the difference in days between date of birth and date of first study drug administration.
- The BMI in kg/m² will be calculated using the following formula:
$$BMI = W / (H * H)$$

where W is weight in kg, and H is height/length in m.

- The Body Surface Area (BSA in m²) will be calculated using Du Bois's formula

$$BSA = 0.007184 \times W^{0.425} \times H^{0.725}$$

where W is weight in kg, and H is height in cm.

All inclusion and exclusion information will be listed only.

5.5 Medical History

Medical History and Concurrent conditions will be coded using MedDRA, version 18.1 or higher.

The number and percentage of subjects with past medical conditions, i.e. not ongoing at baseline, grouped by MedDRA SOC will be displayed by cohort and overall for the safety population. A similar summary will be produced for concurrent medical conditions, i.e. ongoing at baseline.

However, these frequency tables (n and %) will only be provided if the number of events make such a table useful information.

5.6 Physical Examination

The number and percentage of subjects with normal/abnormal physical examination will be displayed over time for each body system as indicated in the CRF and for each cohort and overall in the safety population.

Shift tables comparing baseline (visit 1) ratings with the ratings at the interim visits will be presented for each category by cohort and overall. These shift tables may be omitted if not useful.

The following categories will be examined: skin, ears, nose, throat, lungs, heart, abdomen, back, genital status, basic nervous system and other.

5.7 Protocol Deviations

The number and percentage of subjects for each category of the protocol deviations will be summarised for the safety population.

Again, this table will be omitted if not useful.

5.8 Prior and Concomitant Medications

Prior and Concomitant Medications will be coded using WHO-DRL and will be assigned to the first corresponding ATC code. All medications will be listed for the safety population.

Prior medications are those medications stopped before the intake of the first dose of study Infacort[®] and concomitant medications are those medications taken after intake of the first dose of study Infacort[®]. Prior medications will only be listed.

The number and percentage of subjects with concomitant medications at baseline (i.e. medications intake started before baseline) classified by ATC levels 2 and 3 will be displayed by cohort and overall in the safety population. A similar summary will be produced for concomitant medications started after baseline (i.e., after intake of Infacort[®]).

However, these frequency tables (n and %) will only be provided if the number of events make such a table useful information.

5.9 Extent of Exposure

Compliance regarding the intake of Infacort[®] will be calculated on the basis of the number and strength of capsules dispensed, the number and strength of capsules returned, the number of days between the two visits and the daily dose of Infacort[®] prescribed for the time interval.

The actual daily dose of Infacort[®] taken will be calculated as the amount of Infacort[®] dispensed minus the amount of Infacort[®] returned divided by the number of days between the visits. The difference between planned daily dose and actually dose taken will also be calculated. Descriptive statistics for all variables will be produced by visit and overall grouped by cohort and overall for the safety population. In addition, a summary of the number and percentage of subjects who took less than 75% of the prescribed Infacort[®] dose and their main reasons will be presented for each cohort and overall by visit and overall. A similar summary will show the number and percentage of subjects who took more than the prescribed Infacort[®] dose. In addition, the number of days subjects received a correct treatment of Infacort[®] will be summarized by visit and overall.

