## 8.13 Sick Day Rules

All subjects will be supplied with “Sick day rules” (an example is provided in Appendix 3). When these rules are implemented for a subject, the number of days they are used must be documented.

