#### ***Fever***

>38°C - double oral hydrocortisone dose as long as body temperature continues to be elevated

>39°C - triple oral hydrocortisone dose as long as body temperature continues to be elevated

>40°C - increase oral hydrocortisone dose 5-fold as long as body temperature continues to be elevated

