### **IMP**

The Charité Investigator will issue a prescription for Infacort® to the Charité Pharmacy either calculated from that dispensed at the previous visit, or from information provided by the local physician, and with the necessary overage to allow for both repeated dosing in the case of incomplete administration and any increases in dose in the event of the necessity for implementation of sick day rules. The Charité Pharmacy will dispense the prescription for collection and transport either by courier to the Charité Investigator at the remote site or by the Charité Investigator him-/herself. Temperature monitoring during transport to the remote site in either event, included with the IMP shipment, will be downloaded by either the courier or the Charité Investigator and provided to the Sponsor to confirm that the transportation conditions were acceptable prior to administration and supply of the IMP to the subject. All unused medication and empty (used) Infacort® capsules that are returned by the subject's parents/carers at each visit will be sent by the Charité Investigator to the Charité Pharmacy in Berlin for the purpose of IMP accountability verification.

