7.1 Demographic and Baseline Characteristics

Table 1.1	Subject disposition – Screening population
Table 1.2	Reasons for study discontinuation – Safety population
Table 1.3	Protocol deviations – Safety population
Figure 1	Subject disposition – Screening population
Table 2.1	Gender, ethnicity, ethnic origin, age [days] and causes of adrenal insufficiency – Safety population
Table 2.2	Height, weight, body mass index, body surface area – Safety population
Table 3.1	Past medical conditions (MedDRA system organ classes) – Safety population
Table 3.2	Concurrent medical conditions (MedDRA system organ classes) – Safety population
Table 4.1	Physical examination over time – Safety population
Table 4.2	Physical examination change from baseline – Safety population
Table 5.1	Concomitant medications at baseline at ATC levels 1 and 2 – Safety population
Table 5.2	Concomitant medications started after baseline at ATC levels 1 and 2 – Safety population
Table 6.1	Extent of Exposure – Safety population
Table 6.2	Administration problems, less than 75% intake – Safety population
Table 6.3	Administration problems, more than the prescribed dose – Safety population
Table 6.4	Number of days with a correct intake of Infacort [®] - Safety population

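### SAP 5.9 has no term for sick-day dose increases, so a child dosed exactly as directed is counted as taking more than prescribed, and missed maintenance doses can be hidden

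*SAP*

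**What the plan says.** SAP 5.9 (Extent of Exposure) builds compliance from the number and strength of capsules issued and handed back, together with "the number of days between the two visits and the daily dose of Infacort[®] prescribed for the time interval". Actual daily dose is the amount issued less the amount handed back, spread over the days of the interval. The SAP then adds: "The difference between planned daily dose and actually dose taken will also be calculated". Two counts follow. The first is "a summary of the number and percentage of subjects who took less than 75% of the prescribed" dose, with main reasons (Table 6.2). For the second the text reads: "A similar summary will show the number and percentage of subjects who took more than the prescribed" dose. SAP 7.1 lists this as Table 6.3, "Administration problems, more than the prescribed dose", and no tolerance is set. SAP 5.9 also asks for the number of days of correct treatment (Table 6.4) without defining it. Sick days are not mentioned in the section.

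The protocol has these relevant provisions:

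- Section 10.4: the child's hydrocortisone is replaced by Infacort.
- Appendix 3, for sites without their own rules: above 38°C, "double oral hydrocortisone dose as long as body temperature continues to be elevated"; three-fold above 39°C, five-fold above 40°C, and three-fold for vomiting or diarrhoea.
- Appendix 6 (remote sites): the supply includes overage for "any increases in dose in the event of the necessity for implementation of sick day rules".
- Section 8.13: "When these rules are implemented for a subject, the number of days they are used must be documented".
- Section 8.8: the prescribed dose and its changes go into the CRF dosage record, and carers note missed doses on a diary card.

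**The concern.** The two sides of the comparison are not on the same basis. Capsules taken on sick days are part of the amount used. The planned amount, as worded, is the interval's prescribed daily dose multiplied by its length. A carer who raises the dose as instructed therefore produces apparent over-intake.

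Two outputs are affected. Table 6.3 counts intake that followed the instructions as an administration problem. Table 6.2 becomes less sensitive in children who have been ill, because sick-day drug offsets missed maintenance doses in one capsule total. The planned-minus-actual difference has the same bias. Compliance then partly measures how often a child was ill. With at most 24 children, shown by cohort and visit, a few misclassified intervals visibly change the percentages.

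This is separate from spilled capsules and from doses repeated after spitting out or vomiting (Protocol 10.3). Those also raise the ratio, but here the drug was swallowed and was called for.

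**Working it through.** The documents give no compliance figure to reproduce, so the check applies the SAP 5.9 arithmetic directly.

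**Inputs**

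- Interval length L: about 30 days for the first two intervals, then about 91 days (monthly visits for 2 months, then every 3 months; Protocol Table 1). Rounded, ignoring the ±10-day window.
- Multiplier m: 2, 3 or 5 (Protocol Appendix 3, fallback rules; a site's own rules may differ).
- Sick days per interval s: **assumed**, since no expected number is given. Values of 1, 3 and 7 are shown; 7 is a cut-point in the sick-day summary of Protocol 13.3.6.
- Sick-day increases are taken as Infacort, with no spillage or repeat doses.

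Amounts are in daily maintenance doses, so the child's own dose cancels.

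**Step 1. Full adherence under the current formula**

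Compliance = (L + s(m − 1)) / L

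| s, m | L = 30 | L = 91 |
|---|---|---|
| 1 day, ×2 | 31/30 = 103.3% | 92/91 = 101.1% |
| 3 days, ×3 | 36/30 = 120.0% | 97/91 = 106.6% |
| 7 days, ×2 | 37/30 = 123.3% | 98/91 = 107.7% |
| 7 days, ×3 | 44/30 = 146.7% | 105/91 = 115.4% |
| 7 days, ×5 | 58/30 = 193.3% | 119/91 = 130.8% |

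All exceed 100%, so every such child is counted in Table 6.3. Any multiplier above 1 gives the same direction.

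**Step 2. Masking of missed maintenance doses**

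Let a be the fraction of maintenance taken on well days, with sick-day doses taken in full. The child reaches the 75% cut-off when ((L − s)a + sm) / L = 0.75, so a = (0.75L − sm) / (L − s).

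For s = 3 and m = 3:

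- L = 30: (22.5 − 9)/27 = 50.0%
- L = 91: (68.25 − 9)/88 = 67.3%

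A child at exactly these levels shows 75% but took 22.5/36 = 62.5% or 68.25/97 = 70.4% of what was due.

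**Step 3. With the planned amount set to L + s(m − 1)**

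The fully adherent child scores 36/36 or 97/97 = 100% and leaves Table 6.3. The well-day intake at the 75% cut-off becomes (0.75 × 36 − 9)/27 = 66.7% for 30 days and (0.75 × 97 − 9)/88 = 72.4% for 91 days. The masking shrinks but does not vanish, because sick-day and maintenance drug are still pooled. That is the reason to show the two amounts separately.

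**The case against.** The best defence is that the SAP is silent and does not exclude sick days. The prescribed dose for the interval could be read to include temporary changes, since Protocol 8.8 requires all dose changes to be recorded. That reading is possible, but SAP 5.9 does not refer to that record and its wording points to one daily dose per interval. If the broader reading is intended, it should be stated.

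A second defence is that the information appears elsewhere. The over-intake summary is described as similar to one that reports reasons. Sick-day use is summarised by visit (SAP 5.10, Table 7.2) and listed by subject, so with 24 children a reader could match the two. This helps in explaining individual cases. It does not correct the ratio, the difference or the below-75% count.

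Scope is also limited. The overage statement comes from the remote-site appendix. Suppository and intravenous treatment never enter the capsule count. The size depends on an assumed number of sick days. Spillage and repeat doses would leave some noise in Table 6.3 after the correction. All of this stands.

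A reader might go further and infer that a corrected formula would expose carers who did not raise the dose. On maintenance alone with otherwise full intake, such a child does score 100% now. But Protocol 8.13 documents only days on which the rules were used. A carer who did not use them generates no such day, the planned amount stays at maintenance, and the score remains 100% after the correction.

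**Conclusion.** The point holds for the descriptive exposure and compliance outputs. As written, the SAP 5.9 formula gives more than 100% for any fully adherent child with at least one sick-day increase taken as Infacort, counts that child in Table 6.3, and lowers the chance that missed maintenance doses are seen in Table 6.2. The excess runs from 1.1 percentage points (one doubled day in 91) to 20 points (three tripled days in 30), and higher with more sick days. The direction is certain; the size rests on assumed sick-day counts and the fallback multipliers.

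Two stronger readings are not supported. The SAP does not class these children as overdosed: overdose is handled separately in Protocol 10.5 and 12.3.5, and Table 6.3 only counts intake above the prescribed dose. Nor is the primary endpoint compromised: all analyses use the Safety Population, are descriptive, and none is planned to depend on compliance.

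**What to change.** In SAP 5.9, define the planned amount for an interval as the sum over its days of the dose prescribed for that day:

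- On ordinary days, use the prescribed maintenance dose, updated for changes in the dosage record and diary.
- On days when the sick day rules are documented as used, use the increased dose recorded. If it was not recorded, use the site's own rule and flag the value as assumed.

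Use this total for actual/planned, the planned-minus-actual difference, the below-75% count, the above-prescribed count and the definition of correct-treatment days. Show maintenance and sick-day amounts separately in Table 6.1.

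Where the sick-day amount cannot be established, flag the interval and report it apart from both counts. Taking sick days out of the capsule total is not workable, because dispensed minus returned is a single figure per interval.

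The cost is a paragraph of SAP text and a modest derivation. The day count must already be documented. The multiplier is not explicitly required by Protocol 8.13, and it is not stated whether short increases reach the dosage record, so some intervals will rest on an assumed amount or be set aside. The change affects the analysis only and leaves the dosing rules alone.
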